10.1. Efficacy Measures

10.1.1. Efficacy Assessments at Baseline and during Study Treatment

Within 28 days of randomization, baseline tumor measurements will be performed on each patient. Computed tomography (CT), including spiral CT, scans and magnetic resonance imaging (MRI) are the preferred methods of measurement. In addition, bone scintigraphy will be performed for all patients at baseline (within 28 days of randomization). However, prior bone scintigraphy (obtained as part of routine clinical care) within 45 days before Day 1 of Cycle 1 is also acceptable. *For only those patients with bone lesions identified by bone scintigraphy at baseline*, all such lesions will be evaluated at baseline by focused studies (X-ray, CT scan with bone windows, or MRI) to enable serial assessment. *For patients with inoperable locally advanced breast cancer*, MRI scan of the breast will be performed at baseline. *For patients with visible tumor (such as skin lesions)*, photography will be performed at baseline and each photographic image of the tumor should include a ruler.

The CT portion of a positron emission tomography (PET)-CT scan may be used as a method of response assessment if the site can document that the CT is of identical diagnostic quality to a diagnostic CT (with intravenous and oral contrast). A PET scan alone or as part of a PET-CT scan may be performed separately as part of routine clinical care but cannot be used to assess response according to RECIST v1.1.

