10.1.3. Primary Efficacy Measure

The primary efficacy measure is progression-free survival as defined by RECIST Version 1.1 (Eisenhauer et al. 2009) provided in [Attachment 5](#).

Lilly or its designee will collect and store all tumor measurement images on all enrolled patients throughout the study. An independent review of imaging scans will be performed by an independent panel of radiologists.

The PFS time is measured from the date of randomization to the date of objective progression or the date of death due to any cause, whichever is earlier.

For those patients with nonmeasurable, bone only disease (refer to Inclusion Criterion [5]), objective progression will be established if at least 1 of the following criteria is met:

- the appearance of 1 or more new lesions (in bone or outside of bone), or
- unequivocal progression of existing bone lesions.

Pathologic fracture, new compression fracture, or complications of bone metastases will not be considered as evidence of disease progression, unless at least 1 of the above criteria is met.

For those patients with locally advanced disease for whom surgery is performed with no evidence of residual disease post-operatively, objective progression will be established if at least 1 of the following criteria is met:

- local recurrence, or
- new development of metastatic disease.

For those patients with locally advanced disease for whom surgery is performed with evidence of residual disease post-operatively, new baseline measurements should be taken and RECIST applied.

If a patient is not known to have progressed or died at the time of analysis, PFS time will be censored at the last known progression-free assessment. See Section 12.2.7 for detailed censoring rules.

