12.2.7. Primary Outcome and Methodology

The primary endpoint of this study is PFS. PFS time is measured from the date of randomization to the date of investigator-determined objective progression as defined by RECIST v1.1, or death from any cause. Patients who have neither progressed nor died will be censored at the day of their last radiographic tumor assessment (if available) or date of randomization if no post initiation (that is, postbaseline) radiographic assessment is available. The detailed censoring rules are described below (Table JPBL.12.1).

Table JPBL.12.1. Rules for Determining Date of Progression or Censor for Progression-Free Survival

Rule	Situation	Date of Progression or Censor	Outcome
1	No baseline tumor assessments	Date of Randomization	Censored
2	No post baseline assessments and no death	Date of Randomization	Censored
3	No documented progression and no death (with a post-baseline tumor assessment)	Date of last adequate tumor assessment	Censored
4	Patient lost to follow-up (or withdrew consent from study participation) before documented progression or death	Date of last adequate tumor assessment	Censored
5	Documented progression	Date of documented progression. If a tumor assessment was done on multiple days, use the earliest date for that visit.	Progressed
6	Death without documented progression	Date of death	Progressed
7	Documented progression or death after missing ≥ 2 consecutive post-baseline tumor assessments	Date of last adequate tumor assessment before missed assessments or date of randomization, whichever is later	Censored

Note: Progression-free survival and associated outcome is determined by the earliest of the dates above, if more than 1 situation applies.

The PFS analysis to test the superiority of abemaciclib to placebo in improving PFS time will be performed on the ITT population (as defined in Section 12.2.1) and will use the log-rank test stratified by nature of disease (visceral metastases versus bone only metastases versus other) and sensitivity to endocrine therapy (primary resistance versus secondary resistance). In addition, the Kaplan-Meier method (Kaplan and Meier 1958) will be used to estimate the PFS curves as well as PFS rates at every 3 months for each treatment group. These rates will be compared based on a normal approximation for the difference between the rates.

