- c Visible tumor (such as skin lesions) should be documented by photography and each photographic image of the tumor should include a ruler. For patients who discontinue study treatment without objectively measured progressive disease (PD), continue to evaluate tumor response approximately every 8 weeks for the first 12 months following randomization and thereafter approximately every 12 weeks by the same method used at baseline and throughout the study until the patient has objective disease progression or until study completion. After the patient has objective disease progression, tumor assessments are no longer required and the patient will continue with post-discontinuation follow-up until the patient's death or overall study completion.
- d Survival information is collected at baseline and during both study treatment and postdiscontinuation follow-up. During Long-Term Follow-Up, survival information is collected approximately every 12 weeks for the duration of this period. Although preferable to collect during a clinic visit, survival information may be collected by contacting the patient or family directly (for example, via telephone). Long-Term Follow-up data collection may include anticancer therapies.
- e A local ECG (no replicates required) should be obtained at baseline (Day -14 to Day -1), 2 to 4 hours after the LY dose on Cycle 1 Day 1, upon arrival at site but prior to fulvestrant dose on Cycle 1 Day 15, 2 to 4 hours after the LY dose on Cycle 4 Day 1, and at the short-term follow-up visit.
- f Data on SAEs that occur before the end of trial will be stored in the collection database and the Lilly Safety System. During Long-Term Follow-Up, only SAEs that are related to study drugs or protocol procedures will be collected. All adverse events possibly related to study drugs or protocol procedures should be followed until they resolve, are no longer considered to be possibly related, become stable or return to baseline, the patient starts a new therapy, the patient expires, or the patient becomes lost to follow-up. The frequency of evaluation is determined according to the judgment of the investigator.

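### PFS censoring Rule 4, read with the earliest-date note, overrides Rule 6 for deaths learned of after loss to follow-up or withdrawal, in conflict with the PFS definition

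*Protocol*

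**What the plan says.** Protocol Section 10.1.3 measures PFS "from the date of randomization to the date of objective progression or the date of death due to any cause", whichever comes first. It censors only patients who, at the time of analysis, are not known to have progressed or died, and it refers to Section 12.2.7 for the detailed rules. The sentence introducing Table JPBL.12.1 there takes the same line: it censors patients with neither event, at the last radiographic assessment, or at randomization if there was none after baseline.

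The rules that matter in the table are:

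- Rule 2, "No post baseline assessments and no death": censored at randomization.
- Rule 3, neither progression nor death, with a post-baseline assessment: censored at the last adequate assessment.
- Rule 4, "Patient lost to follow-up (or withdrew consent from study participation) before documented progression or death": censored at the last adequate assessment.
- Rule 6, "Death without documented progression": event at the date of death.
- Rule 7, progression or death after two or more consecutive missed assessments: censored at "Date of last adequate tumor assessment before missed assessments or date of randomization, whichever is later".

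A note then sets precedence: "Progression-free survival and associated outcome is determined by the earliest of the dates above, if more than 1 situation applies".

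On timing, Section 10.1.1 says: "Within 28 days of randomization, baseline tumor measurements will be performed on each patient". The footnotes to Attachment 1 place the baseline scans between Day -28 and Day -1. Section 10.1.2 says that survival data are collected on all patients, and footnote d of Attachment 1 allows this to be done by contacting the patient or family.

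**The concern.** Rule 4 looks at the patient's status when contact ended. The PFS definition, the introductory sentence and Section 10.1.3 look at what is known at the analysis. The two differ for a patient who is lost or withdraws event-free and is later found to have died. That patient meets both Rule 4 and Rule 6, and the note always selects Rule 4 because the last scan precedes the death. A death that the primary endpoint defines as an event then becomes a censored observation. OS has no such rule (protocol Section 10.1.4; SAP addendum Section 4.2), so the same death counts there.

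Two programmers could build different primary datasets, one from Section 10.1.3 and the other from the table. The central-review analysis would not expose the difference, because Section 12.2.9 applies the same table to it. The interim unblinding criteria in Section 12.2.15.2 draw on both PFS analyses.

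There is a second, smaller conflict. Rule 4 has neither Rule 3's requirement for a post-baseline scan nor Rule 7's randomization floor. With no post-baseline scan, its date can fall before randomization.

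**Working it through.** **Design figures.** Inputs from protocol Section 12.1: 378 events, hazard ratio 0.703, 2:1 allocation, 1-sided alpha 0.025. By Schoenfeld's formula, z = √(378 × 2/3 × 1/3) × |ln 0.703| − 1.960 = 9.165 × 0.3524 − 1.960 = 1.270. Power is therefore 89.8%, against about 90% stated. The censoring rate is 1 − 378/630 = 40%, as stated. The denominators 378 and 630 can be relied on.

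**Rules applied literally.** Times are days from randomization. The baseline scan is put at day −20 (an assumption within the permitted window), and scans are due about every 8 weeks.

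| Patient | Rule 4 | Competing rule | Note selects | PFS definition or introductory sentence |
|---|---|---|---|---|
| 1. Clear scans at 56 and 112, lost at 130, died at 160 | Censored 112 | Rule 6: event 160 | Censored 112 | Event 160 |
| 2. Clear scan at 57, lost at 80, died at 130 | Censored 57 | Rule 6: event 130 | Censored 57 | Event 130 |
| 3. No post-baseline scan, lost at 30, no known death | Censored −20 | Rule 2: censored 0 | Censored −20 | Censored 0 |
| 4. No post-baseline scan, lost at 30, died at 70 | Censored −20 | Rule 6: event 70 | Censored −20 | Event 70 |

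Patient 1 missed no scan (the next was due near day 168). Patient 2 missed only the Cycle 5 scan (about day 113), and patient 4 only the first scan (about day 56). Rule 7 therefore applies to none of them.

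The results for patients 3 and 4 also require the baseline scan to count as an adequate assessment, a term that the supplied documents do not define. Rule 7's floor suggests that a pre-randomization date was thought possible. Patient 3 has no effect on the log-rank test at −20 or at 0, because she is never at risk at an event time. Patient 4 loses an event.

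**What Rule 4 adds to Rule 7.** With a clear scan at 56, loss at 70 and death at 200, two assessments were missed, and Rules 4 and 7 both censor at 56. So Rule 4 changes the outcome only for deaths before a second missed assessment, roughly 16 weeks after the last scan on the 8-week schedule.

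**Size.** The documents give no loss rate, so 3% to 8% of 630 leaving before progression is an assumption. The introduction (Section 5) gives a median OS of 2 to 3 years for metastatic breast cancer. With exponential survival and 16 weeks = 112/365.25 = 0.307 years:

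- Median 3 years: 1 − 2^(−0.307/3) = 6.8%
- Median 2 years: 1 − 2^(−0.307/2) = 10.1%
- Low: 630 × 0.03 × 0.068 = 1.3 deaths; 1.3/378 = 0.3%
- High: 630 × 0.08 × 0.101 = 5.1 deaths; 5.1/378 = 1.3%

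After the first year scans are 12 weeks apart and the window is about 24 weeks (0.460 years). If every leaver were on that schedule, the death shares would be 10.1% and 14.7%, giving 630 × 0.03 × 0.101 = 1.9 to 630 × 0.08 × 0.147 = 7.4 deaths.

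**Power.** The final analysis is triggered by 378 counted events, so nominal power stays at 89.8%. Uncounted deaths delay the trigger slightly.

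**The case against.** The strongest reply is that the surrounding text governs. Section 10.1.3 and the introductory sentence both make censoring depend on there being no known event, so Rule 4 should be read as covering patients whose last known status is event-free. A patient whose death the family reports is arguably not lost for vital status. This is a reasonable account of what was probably meant, but it does not remove the conflict. Section 10.1.3 defers to the table for detail, Rule 4 speaks of status before death, and withdrawal of consent does not lapse when a death is reported. On this reading Rule 4 also adds nothing to Rules 2 and 3 for patients with baseline imaging.

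Other parts of the reply stand:

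- The documents do not say specifically that deaths are collected for patients who withdraw from the study altogether. Footnote d does not mention them.
- For a patient with no post-baseline scan and no death, Rule 2 and the introductory sentence both give randomization. Only the note overrides them. A reader might infer that negative times distort the primary test, but without a death they cannot move the log-rank statistic, and an effect on the number analyzed is speculation about software.
- The supplied SAP is an addendum on OS. It cites a main SAP (v4) that was not available, and protocol Section 12.2.2 allows the SAP to carry clarifications. SAP v4 may define the terms or set the order of the rules.

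**Conclusion.** As written, the table contradicts the PFS definition for a known death after loss or withdrawal when fewer than two assessments were missed. The missing randomization floor is a secondary wording conflict, which matters only if a baseline scan counts as adequate and a death follows.

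The numerical effect is probably small: about 1 to 5 deaths, or 0.3% to 1.3% of 378. This rests on the assumed 3% to 8% loss and on general mortality for the disease. It would be larger if those who leave are sicker than average or leave after the first year.

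The documents do not support three stronger readings:

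- A reader might infer that the plan deliberately discards known deaths. It contradicts itself on the point and does not settle it.
- A reader might infer a tilt toward abemaciclib. The documents give no difference in dropout between arms, so the direction is unknown.
- A reader might suppose that 30% of leavers die in the window, giving 630 × 0.08 × 0.30 = 15.1 deaths (4.0%). That is about three to four times the mortality implied by Section 5, and nothing in the documents supports it.

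**What to change.** Reword Rule 4 along these lines: *lost to follow-up or consent withdrawn, with neither progression nor death known at the data cutoff; censored at the later of randomization and the last adequate post-baseline assessment.* Known progressions and deaths then fall to Rules 5, 6 or 7, and Rule 4 agrees with Rules 2 and 3. The overlap with those two rules is harmless.

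Keep the earliest-date note, because it is what lets Rule 7 take precedence over Rules 5 and 6. Use the same wording for the central-review PFS analysis. If SAP v4 already resolves the point, align the protocol table with it.

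If the PFS analysis has already been run, list the patients censored under Rule 4 who have a recorded death and repeat the analysis under the revised rule.

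The cost is one table row. No new data or patients are needed.

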12.2.8. Secondary Outcomes and Methodology

The secondary objectives can be found in Section 6.2.

12.2.8.1. Overall Survival

OS is an important secondary endpoint for this study. To maintain the study-wise type I error rate, OS will be hierarchically tested; that is, OS will only be tested inferentially for significance only if the test of PFS is significant. Further details will be in the SAP.

12.2.8.2. Objective Response Rate, DCR, CBR, and DoR

The objective response rate, DCR, and CBR of each treatment arm will be calculated as defined in Section 10.1.4 using the ITT population. All rates will be compared between treatment arms based on a normal approximation for the difference between the rates.

The DoR time is defined only for responders (patients with a best response of CR or PR). It is measured from the date of first evidence of CR or PR to the date of objective progression or the date of death due to any cause, whichever is earlier. A Kaplan-Meier analysis of DoR will be performed to estimate the DoR curve for each arm.

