- [3] have postmenopausal status due to either surgical/natural menopause or ovarian suppression (initiated at least 28 days prior to Day 1 of Cycle 1) with a gonadotropin-releasing hormone (GnRH) agonist such as goserelin. Postmenopausal status due to surgical/natural menopause requires at least 1 of the following:
- prior bilateral oophorectomy
 - age ≥ 60 years
 - age < 60 years and amenorrheic for at least 12 months (in the absence of chemotherapy, tamoxifen, toremifene, or ovarian suppression) and follicle-stimulating hormone (FSH) and estradiol levels in the postmenopausal range
- [4] have a negative serum pregnancy test at baseline (within 14 days prior to randomization) and agree to use medically approved precautions to prevent pregnancy during the study and for 12 weeks following the last dose of abemaciclib if postmenopausal status is due to ovarian suppression with a GnRH agonist
- [5] have either measurable disease or nonmeasurable bone only disease. Measurable and nonmeasurable disease are defined according to the Response Evaluation Criteria in Solid Tumors (RECIST Version 1.1 [v1.1], Eisenhauer et al. 2009; refer to [Attachment 5](#)). Nonmeasurable bone only disease may include any of the following: blastic bone lesions, lytic bone lesions without a measurable soft tissue component, or mixed lytic-blastic bone lesions without a measurable soft tissue component.
- [6] are female and ≥ 18 years of age
- [7] have given written informed consent prior to any study-specific procedures
- [8] have adequate organ function, including:
- hematologic: absolute neutrophil count $\geq 1.5 \times 10^9/L$, platelets $\geq 100 \times 10^9/L$, and hemoglobin ≥ 8 g/dL. Patients may receive erythrocyte transfusions to achieve this hemoglobin level at the discretion of the investigator; however, initial study drug treatment must not begin earlier than the day after the erythrocyte transfusion.
 - hepatic: bilirubin ≤ 1.5 times upper limit of normal (ULN) and alanine aminotransferase (ALT) ≤ 3.0 times ULN
 - renal: serum creatinine ≤ 1.5 times ULN
- [9] have a performance status ≤ 1 on the ECOG scale

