9.3. Method of Assignment to Treatment

Upon obtaining informed consent, site personnel should access the interactive web response system (IWRS) which will assign a patient number. Patients who meet all criteria for enrollment will be randomly assigned to receive either abemaciclib plus fulvestrant or placebo plus fulvestrant. Assignment to treatment groups will be determined by a computer-generated random sequence using the IWRS.

Randomization will be stratified by the following: nature of disease (visceral metastases versus bone only metastases versus other) and sensitivity to endocrine therapy (primary resistance versus secondary resistance).

The IWRS will be used to assign abemaciclib/placebo and fulvestrant (where supplied). Site personnel will confirm that they have located the correct study medication packages by entering a confirmation number found on the packages into the IWRS.

The period between randomization to blinded study drug in IWRS and the first dose (Cycle 1 Day 1) should not exceed 7 days.

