The 2-look group-sequential design of the primary endpoint will be used to accommodate an event-driven plan for the interim and final analyses. There is 1 planned interim analysis and 1 final analysis for PFS in this study. The interim analysis is planned to take place after

approximately 265 (approximately 70% of the planned) investigator-assessed PFS events have occurred. The cumulative 1-sided type I error rate of .025 will be maintained using the following method. At the interim analysis, the nominal significance level will be .00001. The remaining alpha will be spent at the final analysis. The resulting boundary p-value for the final analysis is dependent on the exact number of events observed at each analysis and can be calculated using the method of Slud and Wei (1982). If the analyses are performed at exactly 265 and 378 events, then the boundary p-value at the final analysis will be .02499996).

The actual boundary for the final analysis will be calculated based on the actual number of events observed at the time of each analysis using software that implements the α -spending scheme noted above (for example, ADDPLAN 6.0, SAS 9.2, or similar software).

If statistical significance is not observed at the interim analysis, the final PFS analysis will be performed after 378 PFS events have been observed in the ITT population based on investigator assessment. Once statistical significance is declared at the interim analysis or the final analysis, the study will be positive based on the primary endpoint of PFS, and testing of secondary endpoints will proceed as described in the SAP.

The interim PFS analyses will be performed by DMC. The requirements for unblinding the sponsor at the interim analyses are found in Section 12.2.15.

The primary test of PFS will compare the 2 treatment groups using a log-rank test stratified by the randomization factors.

A stratified Cox proportional hazard model (Cox 1972) with treatment as a factor will be used to estimate the HR and corresponding 95% CI with Wald's test p-value after adjusting for the same randomization variables specified for the primary analysis. An additional unstratified Cox regression model will be employed to explore the effects of prognostic variables, such as of the stratification variables and intrinsic/extrinsic factors, on treatment response.

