It is assumed that at each protocol-specified time point, a response assessment occurs. (When no imaging/measurement is done at all at a particular time point, the patient is not evaluable (NE) at that time point.) Table 1 provides a summary of the overall response status calculation at each time point for patients who have *measurable disease* at baseline.

Table 1. Time Point Response: Patients with Target (\pm Nontarget) Disease

Target Lesions	Non-Target Lesions	New Lesions	Overall Response
CR	CR	No	CR
CR	Non-CR/non-PD	No	PR
CR	Not evaluated	No	PR
PR	Non-PD or not all evaluated	No	PR
SD	Non-PD or not all evaluated	No	SD
Not all evaluated	Non-PD	No	NE
PD	Any	Yes or No	PD
Any	PD	Yes or No	PD
Any	Any	Yes	PD

Abbreviations: CR = complete response; PR = partial response; SD = stable disease.; PD = progressive disease; NE = inevaluable.

Table 2 is to be used when patients have *nonmeasurable* disease only.

Table 2. Time Point Response: Patients with Nontarget Disease Only

Nontarget Lesions	New Lesions	Overall Response
CR	No	CR
Non-CR/non-PD	No	Non-CR/non-PD ^a
Not all evaluated	No	NE
Unequivocal PD	Yes or No	PD
Any	Yes	PD

Abbreviations: CR = complete response; PD = progressive disease; NE = inevaluable.

^a non-CR/non-PD is preferred over SD for nontarget disease.

Frequency of Tumor Re-Evaluation

A baseline tumor evaluation must be performed within 4 weeks before patient begins study treatment. Frequency of tumor re-evaluation while on and adapted to treatment should be protocol-specific and adapted to the type and schedule of treatment. In the context of Phase 2 studies where the beneficial effect therapy is not known, follow-up every 6-8 weeks is reasonable. Normally, all target and non-target sites are evaluated at each assessment using the same method. However, bone scans may need to be repeated only when CR is identified in target disease or when progression in bone is suspected.

Confirmatory Measurement/Duration of Response

Confirmation:

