4.1. Background

Overall survival (OS) is an important secondary endpoint for this study. A gate-keeping strategy will be utilized to control the overall type I error at 0.025 (one-sided) for the secondary endpoint OS. That is, OS will be tested only if progression free survival (PFS) is significant. More details concerning gatekeeping and alpha spending across multiple analyses of OS are provided in JPBL SAP v4 Section 6.7.3.3.

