At each analysis, the null hypothesis above will be tested using a 1-sided stratified log rank test, stratified by nature of disease and prior sensitivity to endocrine therapy.

The cumulative 1-sided type I error rate of .025 will be maintained using the Lan-Demets method. Specifically, an α -spending function corresponding to the following O'Brien-Fleming type stopping boundary will be used for this interim efficacy analysis:

$\alpha^*(t_k) = 2 (1 - \Phi) ^{(1-\Phi)}$	$\int \Phi^{-1} (1 - \alpha / 2)$	}.
	$\sqrt{t_k}$	

Here, t_k is the information fraction at time k, Φ is the standard normal cumulative distribution function, and Φ^{-1} is the standard normal quantile function. The boundary p-value at each analysis will be calculated based on the actual number of events observed at the time of analysis using software that implements this alpha-spending function (for example, ADDPLAN 6.0 or SAS 9.2, or East 6.0). Leo Document ID = 6014b4cb-c936-4a51-91a7-2309da1ee52e

Approver: Approval Date & Time: 25-Aug-2017 15:41:09 GMT Signature meaning: Approved

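### ORR is compared with no randomization strata named, unlike the PFS and OS tests; under assumed bone-only shares and response rates its 95% CI is about 2–6% too wide

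*Protocol*

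**What the plan says.** Protocol 12.2.8.2 analyses ORR, DCR and CBR in the ITT population and states: "All rates will be compared between treatment arms based on a normal approximation for the difference between the rates". It names no strata and no stratified estimator.

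The time-to-event tests differ. Protocol 12.2.7: "The primary test of PFS will compare the 2 treatment groups using a log-rank test stratified by the randomization factors". SAP addendum 4.3, for OS: the null hypothesis "will be tested using a 1-sided stratified log rank test, stratified by nature of disease and prior sensitivity to endocrine therapy". These are the factors used at randomization (Protocol 9.3): "Randomization will be stratified by the following: nature of disease (visceral metastases versus bone only metastases versus other) and sensitivity to endocrine therapy".

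Three other provisions bear on ORR:

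- Inclusion criterion 5 (Protocol 7.1) requires that patients "have either measurable disease or nonmeasurable bone only disease".
- Attachment 5 has a separate grid, "Table 2. Time Point Response: Patients with Nontarget Disease Only", whose outcomes are CR, non-CR/non-PD, not evaluable and PD. It has no PR.
- Protocol 12.2.7 says that after a positive PFS result "testing of secondary endpoints will proceed as described in the SAP". The only SAP supplied is the OS addendum, which does not mention ORR and points elsewhere (section 4.1): "More details concerning gatekeeping and alpha spending across multiple analyses of OS are provided in JPBL SAP v4".

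**The concern.** Stratified 2:1 randomization balances the arms on nature of disease. An unstratified variance for the difference in rates still includes the variation between strata, so the interval is wider and the test weaker than they need be. The loss depends on how far the response rate differs between strata.

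For ORR that difference is partly built into the endpoint. Criterion 5 leaves nonmeasurable bone-only disease as the only route into the trial for a patient without measurable disease, so all such patients are in one randomization stratum. They stay in the ITT denominator, and only a CR can make them responders. The stratum's ORR need not be zero, because bone lesions with a measurable soft-tissue component can also be bone-only disease.

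At stake is a little precision and power on one secondary endpoint. The unstratified difference is not biased, and leaving out the strata does not raise the false-positive rate. DCR and CBR should be almost unaffected.

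**Working it through.** **The plan's own figure.** The documents give no power or CI width for ORR. The one sizing figure, PFS power, reproduces: Φ(√(378 × 2/9) × (−ln 0.703) − 1.96) = Φ(9.165 × 0.3524 − 1.96) = Φ(1.27) = 0.898, against about 90% in Protocol 12.1.

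**Inputs from the documents.** 630 patients randomized 2:1 (Protocol 8.1, 12.1), taken as 420 and 210; two-sided 95% intervals and alpha 0.05 (12.2.2).

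**Evidence on stratum ORR.** Protocol 5.1.1 reports, for the phase 1 fulvestrant combination cohort of 19, 4 responses, or 36.4% of the 11 patients with measurable disease. Since 4/11 = 36.4%, none of the other 8 responded. This is weak: another study, and an exact 95% upper limit for 0/8 of 1 − 0.025^(1/8) = 37%.

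**Assumed.** The bone-only share s, and the ORR in bone-only and other patients by arm.

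**Formulas.** With pA and pC the overall arm rates:

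- Unstratified: Vu = pA(1−pA)/420 + pC(1−pC)/210.
- Stratified: Vs replaces each p(1−p) by s·pb(1−pb) + (1−s)·po(1−po), where pb and po are that arm's bone-only and other rates.
- Half-width = 1.96√V; excess width = √(Vu/Vs) − 1.

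**One case in full** (25% bone-only at 2%; others 20% vs 32.4%):

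- pA = 0.25 × 0.02 + 0.75 × 0.324 = 0.248; pC = 0.25 × 0.02 + 0.75 × 0.20 = 0.155.
- Vu = 0.186496/420 + 0.130975/210 = 0.0010677.
- Vs = 0.169168/420 + 0.1249/210 = 0.0009975.
- Half-widths 6.40 and 6.19 points; √1.0704 − 1 = 3.5%.

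**All cases** (rates are control vs abemaciclib; a single rate applies to both arms):

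| Bone-only share, ORR | Others' ORR | Half-width, unstratified vs stratified (points) | Excess |
|---|---|---|---|
| 15%, 3% | 20 vs 32% | 6.68 vs 6.56 | 1.9% |
| 25%, 2% | 20 vs 32.4% | 6.40 vs 6.19 | 3.5% |
| 30%, 0% | 25 vs 37% | 6.63 vs 6.24 | 6.3% |
| 25%, 10 vs 16% | 17.3 vs 27.7% | 6.40 vs 6.37 | 0.5% |
| 25%, 5 vs 8% | 19 vs 30.4% | 6.40 vs 6.28 | 1.9% |
| 42% (8/19), 0% | 24 vs 36.4% | 6.09 vs 5.62 | 8.4% |
| 42% (8/19), 0% | 30 vs 45% | 6.62 vs 5.95 | 11.4% |

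Equal ORR across strata gives 0%. In the first three rows Vu/Vs is 1.04, 1.07 and 1.13, equivalent to about 4%, 7% and 13% more patients.

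**Sensitivity to the other patients' ORR**, with bone-only 15–30% at 0–3%: 2.1–6.2% at 36.4% on abemaciclib and 15–25% on placebo; 1.1–3.3% at 25% and 10%; 3.7–8.6% at 50% and 25%.

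**Simulation** (300,000 trials, three strata, random stratum totals, 2:1 within stratum, weights nA·nC/(nA+nC)), first three rows in order:

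| | Row 1 | Row 2 | Row 3 |
|---|---|---|---|
| Type I error, unstratified | 0.046 | 0.043 | 0.037 |
| Type I error, stratified, plain variance | 0.052 | 0.052 | 0.052 |
| Type I error, stratified, n−1 | 0.050 | 0.051 | 0.051 |
| Power, unstratified (%) | 84.6 | 81.1 | 70.6 |
| Power, stratified, n−1 (%) | 85.3 | 82.6 | 74.4 |
| Power, stratified, calibrated to 0.05 (%) | 85.2 | 82.4 | 74.2 |

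Against the calibrated test, the power lost is 0.6, 1.3 and 3.6 points. The unstratified type I error depends on the null rates chosen: with both arms at the control rates it was 0.042–0.049, still conservative. At bone-only ORR of 10 vs 16% there is no power gain (80.5% unstratified vs 80.3% calibrated). With six strata (25% primary resistance assumed; 100,000 trials), type I error is 0.053–0.054 with the plain variance and 0.050–0.052 with n−1.

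**The case against.** The strongest reply is that nothing is wrong. An unstratified difference in proportions is valid under stratified randomization, and its simulated coverage is 95.3–95.9% (others at 36.4% and 20%). No ORR power target or alpha allocation is given in the supplied text. This stands, and is why the point is only an improvement.

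Second, a stratum-weighted difference is itself a normal approximation, so the sentence does not exclude strata, and SAP v4 may specify them. This also stands; the conclusion covers only the protocol and the addendum.

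Third, Protocol 12.2.7 compares the 3-monthly PFS rates in the same way, so the protocol is consistent: log-rank tests stratified, rates not. That is true, but the case here rests on how response is defined by measurability, which does not carry over to PFS rates.

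Fourth, 2–6% depends on the ORR outside bone-only disease, which the documents do not give for this trial. Holding 20 vs 32% there, 30% bone-only at 0% gives 5.0% rather than 6.3%. This stands, as does the objection that 8/19 from a phase 1 cohort is thin support for the upper end: nothing shows those 8 patients had bone-only disease.

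Fifth, n−1 denominators might remove part of the gain. Inflating Vs by n/(n−1) would give 1.4, 2.9 and 5.7% with three strata. But the expectation of p̂(1−p̂)/(n−1) is p(1−p)/n, so Vs above already describes the n−1 estimator. Simulated excess widths with it are 1.7, 3.3 and 6.1%. This does not stand.

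**Conclusion.** The point holds as a low-severity improvement. On the supplied text, the ORR comparison does not use the randomization strata, and the protocol's own eligibility and response rules make a difference in ORR between strata likely. The three main assumed mixes give a 95% CI 1.9–6.3% too wide; the wider set of assumptions runs from 0% to 11.4%. The direction is conservative, so a real ORR difference is slightly harder to show. Confidence is medium, because every stratum share and rate is assumed and SAP v4 has not been seen.

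**What to change.** In Protocol 12.2.8.2, state that ORR is compared by a stratum-weighted risk difference, with a within-stratum standard error using n−1 denominators and a 95% CI. Stratify by nature of disease, or by both randomization factors with a prespecified rule for pooling sparse cells. If SAP v4 already does this, a cross-reference is enough. DCR and CBR may follow the same method for consistency, with negligible gain expected. The 3-monthly PFS rates in 12.2.7 can stay as they are.

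The cost is one sentence, one program option and the pooling rule. There are two drawbacks. The stratified Wald test runs slightly above nominal with the plain variance (0.052–0.054), which n−1 denominators bring to 0.050–0.052. The weighted difference also need not equal the simple difference between the two reported arm ORRs, so the report should say which one is shown.
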